**Table 2**

	Screening phone call	Baseline Week 0	Treatment Phase Weeks 1 - 6	Follow-up Week 6 (- 2 days/+5 days)	Follow-up Week 12 (- 2 days/+5 days)	Follow-up Week 24 (- 2 days/+5 days)
Phone Screen	X					
Screening Survey	X					
BFI	X	X		X	X	X
PHQ-2	X					
Consent	X					
Pt. Info & Dem.	X					
Concomitant of Medications		X				
Diagnosis & Treatment of initial cancer		X				
FACT-O		X		X	X	X
PSQI		X		X	X	X
PROMIS		X		X	X	X
IPAQ		X				
SCQ		X				
FSQ		X				
MAIA		X		X		
Daily Logbook			X			
Acupressure Fidelity				X		
Assessment of blinding				X		
AcuWand Comfort				X		
Final Evaluation						X

**Administering Study Assessments.** All potential participants will be screened over the phone using a brief questionnaire to confirm eligibility for the study. Enrolled participants will then receive an email link to their RedCAP study measures at baseline, weeks 0, 6, 12 and 24. All the surveys will be administered at all-time points with the exception of descriptive and baseline assessments, which will only be collected at week 0; fidelity, blinding and adherence, which will only be asked at week 6; and a final evaluative questionnaire about the participants' perception of the study and the use of the AcuWand device. Adverse events will be collected at all-time points. Inspirational reminder emails, texts, or phone calls (as appropriate for a given participant) will be made to encourage the highest possible response rate to each round of study assessments. Participants without an email account will be assisted in obtaining a free Gmail account and how to access it on their computer tablet by study staff. Those participants who do not have access to Wi-Fi will be assisted in finding free Wi-Fi in their community (e.g., public library, Starbucks, McDonalds, etc.) IT study staff will be available to assist participants with any questions that may arise. E-mail is required so that study instruments may be accessed through surveys in RedCAP.

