**Screening.** All potential participants will be screened over the phone using a basic questionnaire to confirm their eligibility. Specifically, an abbreviated form of the *Patient Health Questionnaire (PHQ-2)* will be used to detect untreated depression, and the *Brief Fatigue Index (below; BFI)* will be used to determine fatigue. These measures will be collected before consent and enrollment in to the study and will therefore be kept to the absolute minimum to determine eligibility.

Rescreening. Participants may be rescreened at 6 weeks after initial screening if they failed their initial screening based on: stable chronic medications and no new planned interventions for their fatigue or cancer.

**Fatigue Measure (administered at screening and weeks 0, 6, 12, 24).** *Brief Fatigue Inventory (BFI)* will be used to assess the severity and impact of fatigue on daily functioning. The BFI is a scale validated in cancer patients with an alpha coefficient exceeding 0.95, which correlates well with other fatigue measures. The BFI assesses severity and impact of fatigue in cancer patients over the past 24 hours. The instrument consists of 9 items, each measuring fatigue on a 0-10 scale, and is calculated from the mean of completed items. Scores of  $\geq 4$  indicate clinically- relevant fatigue. A three-point change or a drop below 4 is considered a clinically meaningful change.

**Sleep Quality (administered weeks 0, 6, 12, 24).** *Pittsburgh Sleep Quality Index (PSQI)* is widely used 19-item questionnaire evaluates sleep disturbance over the past month. It yields a total score and 7 component scores: sleep quality; sleep latency; sleep duration; habitual sleep efficiency; sleep disturbances; use of sleep-promoting medication; and daytime dysfunction. In women with breast cancer, Cronbach's alpha for the global PSQI is 0.80. A score  $>7$  in breast cancer patients and thus likely in ovarian cancer patients suggests poor sleep quality. The scale has adequate psychometrics. The primary outcome will be the total PSQI score at baseline and week 6, although we will conduct exploratory analyses on the PSQI subscales.

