**Safety, Fidelity, Blinding and Adherence (administered week 6 except for adverse events and adherence to acupressure, which are collected throughout the study).**

Adverse Events will be graded according to National Cancer Institute Common Toxicity Criteria version 4.03.

Testing Participant Fidelity We will be assessed using two methods. The first, as detailed in our prior study, is done by research staff using a Skype face-to-face call (we will install Skype on the computer tablets and assist participants in using this program as needed.) Participants will be asked to identify the location, stimulation technique, and the amount of pressure (be able to demonstrate correct use of their AcuWand) of their acupoints. The number of acupoints correctly located will be recorded as will the adequacy of stimulating the acupoints (recorded as "yes" or "no"). The percentage of correct answers 0 to 100% will be calculated, based on circular (clockwise or counterclockwise) motion, maintaining contact with skin, and applying pressure such that the nail of the applying finger/thumb blanches. The second method will be data download from the AcuWand via Bluetooth when the computer tablet is connected to Wi-Fi. The AcuWand will be able to provide data on the duration, frequency, and amount of pressure used by participants-it cannot provide data on the location of where participants stimulated their points. We employ both methods to ensure that fidelity is measured across all parameters and in collect redundant measure in case an AcuWand does not transmit data.

Blinding will be assessed by asking participants, which type of acupressure they thought they were performing.

Adherence to Acupressure will be assessed by asking participants to record if and when they performed acupressure, the order in which they performed their acupressure points, and the amounts of achiness and/or tenderness they experienced while performing the acupressure on a Visual Analog Scale daily in the study logbooks. These will be used in association with data downloaded from the AcuWands. Bi-weekly emails will be used to troubleshoot and encourage adherence.

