**Handling Missing Data.** The *linear mixed-effects* framework is an intent-to-treat framework in the sense that it uses all available data at all time-points. So if there are missing outcome values in any phase due to participant dropout, the usual analysis will still be valid. If the proportion of dropouts is substantial (20% or more) in either arm, then we shall also perform a weighted analysis with weights equal to the inverse of the probability of dropout. On the other hand, missing covariate values for the subject-level information will be imputed using multiple imputation methods. All missing values will be imputed using the chained equation method. The advantage of using this technique is its flexibility in allowing different types of variables (categorical and continuous) to be imputed together without requiring any multivariate joint distributional assumption. In this method, the missing values are sequentially updated using bootstrap or Markov Chain Monte Carlo based on multiple regression models with other variables as covariates. This procedure will be carried out for a number of repetitions or cycles, thereby constructing an ‘imputed’ dataset. Ten such ‘imputed’ datasets will be used for the final analysis, a number which is considered adequate for most applications. Finally, we shall combine the results from the ten regressions with the imputed data using Rubin’s formula.

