**Table 3: Mean and standard deviation of changes between baseline and 6 weeks by study arm**

	N	Mean	Std. Deviation
True Acupressure	41	-1.9621	2.04466
Sham Acupressure	45	-1.2988	1.63485
Usual Care	51	-0.4336	1.51849
Total	137	-1.1752	1.82757

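### The plan calls the mixed model valid under dropout without naming the missing-at-random assumption, tests no departure from it, and misstates the fallback weights

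*Combined protocol and SAP*

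**What the plan says.** The paragraph on Handling Missing Data (Statistics Section) argues that the linear mixed model uses all available data, so with missing outcomes from dropout "the usual analysis will still be valid". It does not mention missing at random.

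It plans one safeguard for missing outcomes. "If the proportion of dropouts is substantial (20% or more) in either arm", a weighted analysis is added, with "weights equal to the inverse of the probability of dropout". The predictors of dropout are not named. Multiple imputation is introduced for covariates: "missing covariate values for the subject-level information will be imputed using multiple imputation methods".

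Section 4.1 has the BFI "administered at screening and weeks 0, 6, 12, 24", and the primary model uses weeks 0, 6, 12 and 24. During treatment there is a daily logbook, in which women "record if and when they performed acupressure", with point order and achiness or tenderness, but no BFI. Table 2 gives the next assessment as "Follow-up Week 6 (- 2 days/+5 days)".

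Section 7.2.2 accepts that loss to follow-up may be related to the intervention. Table 3, "Mean and standard deviation of changes between baseline and 6 weeks by study arm", lists 41 true acupressure, 45 sham and 51 usual-care women. I read these as the trial's relaxing, sham and no-treatment arms.

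**The concern.** Using all available data does not by itself make an analysis valid. A likelihood-based mixed model gives unbiased arm comparisons under dropout if, given the data in the model, being missing does not depend on the unseen outcome, and if the model is right. The plan presents this conditional property as unconditional, although section 7.2.2 gives a reason to doubt the condition.

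The assessment schedule sharpens the point. A woman lost for good before week 6 supplies only baseline BFI and covariates. Nothing in the model shows whether she was improving or worsening when she left. Her contribution to the week-6 estimate comes from completers in her arm, adjusted for her own baseline.

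The weighted fallback does not fill the gap. Even with correct weights it would also rest on missing at random. As written it is not a valid inverse-probability analysis, because completers should be weighted by the inverse of the probability of remaining. Its trigger refers to either arm in a three-arm trial. Standard chained-equation imputation assumes missing at random too, should its sentence on all missing values be read to include outcomes.

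At stake is the relaxing versus sham contrast, which section 4.0 relies on to isolate the specific effect of acupressure.

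**Working it through.** **Inputs.** Table 3, mean week-6 change: relaxing −1.9621 (n = 41, SD 2.04466), sham −1.2988 (n = 45, SD 1.63485), usual care −0.4336 (n = 51, SD 1.51849). Section 3.2: 1:1:1 allocation, 57 per arm planned. The number actually randomised per arm is not reported, so 57 is an assumption. If arms were equal, the smallest possible size is 51.

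**Reproducing Table 4.** Pooled SD = √[(40×2.04466² + 44×1.63485² + 50×1.51849²)/134] = 1.728.
- Relaxing − sham: −0.663, SE 1.728×√(1/41 + 1/45) = 0.373, p = 0.078.
- Relaxing − usual care: −1.529, SE 1.728×√(1/41 + 1/51) = 0.362, p < 0.001.

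Both agree with the document.

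**Missing week-6 change, 57 per arm.** Relaxing 16/57 = 28.1%; sham 12/57 = 21.1%; usual care 6/57 = 10.5%; overall 34/171 = 19.9%. The three-arm chi-square gives p = 0.061. Fisher tests give p = 0.031 for relaxing versus usual care and p = 0.51 for relaxing versus sham. With 51 per arm, relaxing is 10/51 = 19.6% and usual care 0%.

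**Reference scenario: missing women take the usual-care mean change.**
- Relaxing: (41×−1.9621 + 16×−0.4336)/57 = −1.533.
- Sham: (45×−1.2988 + 12×−0.4336)/57 = −1.117.
- Usual care: −0.434.

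| | Table 3 | 57 per arm | 51 per arm |
|---|---|---|---|
| Relaxing − sham | −0.66 | −0.42 (37% smaller) | −0.47 (30% smaller) |
| Relaxing − usual care | −1.53 | −1.10 (28% smaller) | −1.23 (20% smaller) |

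**Other scenarios, 57 per arm.**
- Zero change for missing women in all arms: −0.39 and −1.02.
- Zero change for missing sham women only: sham (45×−1.2988)/57 = −1.025, so relaxing − sham widens to −0.94.

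**Tipping points, 57 per arm, other arms as observed.** Let x be the mean change of the 16 missing relaxing women (positive means more fatigue).
- Relaxing = sham: x = (57×−1.2988 + 41×1.9621)/16 = +0.40.
- Relaxing = usual care: x = (57×−0.4336 + 41×1.9621)/16 = +3.48.

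With 51 per arm (10 missing), the same formula gives +1.42 and +5.83.

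All of these are weighted averages of Table 3, not fits of the planned model.

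**Behaviour of the planned model.** A random-intercept model was simulated with true effects −1.5 (versus sham) and −2.5 (versus no treatment), 57 per arm, and 16/12/6 women lost after baseline.

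| Dropout | vs sham | vs no treatment |
|---|---|---|
| Completely at random | −1.49 | −2.51 |
| Depends on baseline BFI (missing at random) | −1.53 | −2.52 |
| Poorer responders leave, every arm | −1.65 | −2.89 |
| Better responders leave, every arm | −1.39 | −2.10 |

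The first two rows are unbiased within simulation error. The last two miss in opposite directions.

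**Weights.** To illustrate, take the usual-care and relaxing rates as two dropout probabilities. Inverse probability of remaining gives 57/51 = 1.12 and 57/41 = 1.39. As written, the weights are 57/6 = 9.50 and 57/16 = 3.56. The order is reversed, so completers least like the women lost would count most.

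**The case against.** A reader might infer that the relaxing effect is overstated, and most in that arm because a 27-minute daily task drives out women it does not help. The documents do not support this. They give no reasons for the missing data. Sham carries the same daily task in an otherwise identical app, and the assumed loss of 16 versus 12 is compatible with chance. If sham lost the non-responders, the relaxing versus sham difference would be understated, as the −0.94 scenario shows.

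Three further points have force.
- A missing week-6 change is not the same as leaving before week 6. Such a woman may still supply weeks 12 and 24, which the model uses. The documents do not say how many of the 34 gave only a baseline.
- The denominators are unreported, and sections 7.2.3 and 7.2.4 allow replacements. If the arms were equal, however, completion is uneven at any size from 51 upward.
- No significant result is shown to be lost. Relaxing versus sham already has p = 0.078, and relaxing versus usual care survives every scenario shown above. The plan also has reminders, telephone completion and three contact attempts.

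Logbook and AcuWand data could inform dropout weights, but the plan does not say they will. These points limit the claim about size and direction. They do not rescue the validity statement, the missing sensitivity analysis or the weights.

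**Conclusion.** The concern holds as a conditional one. The validity statement needs two conditions that the plan omits, no planned analysis examines departures from missing at random, and the fallback weights are misstated. Bias is possible in either direction and is not demonstrated.

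The indicative size depends on equal arms, on the assumed 57 (or 51) per arm, and on missing women behaving like usual care. On that basis, relaxing versus usual care is robust in direction. Relaxing versus sham is the contrast for which the assumption about missing women matters: modest average worsening among the missing relaxing women would remove it. This should be corrected. It does not undermine the primary model as a choice.

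**What to change.** 1. Replace the validity claim with a statement that the analysis is valid if outcomes are missing at random and the model is correctly specified.
2. Define the weights as the inverse probability of remaining, name the predictors, and trigger the weighted analysis at 20% or more dropout in any arm.
3. Add a sensitivity analysis, reported beside the primary result whatever the dropout rate. It should multiply impute missing acupressure outcomes from the no-treatment arm's mean change, and apply a delta tipping point varied separately by arm so that both directions are covered.
4. Report the number randomised per arm, and how many women without week 6 gave later BFI scores.
5. Date the amendment and label it as made after the Table 3 results were seen.

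The cost is a little extra analysis and reporting on existing data, with no new visits or participants.

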## HYPOTHESES AND OBJECTIVES

We are proposing to evaluate the impact of **six weeks of daily self-administered relaxing acupressure** on fatigue, sleep, and quality of life in persistently fatigued ovarian cancer survivors compared to 6 weeks of daily self-administered sham acupressure or no treatment. Survivors who have fatigue starting at or after cancer diagnosis, and have ≥4 on the Brief Fatigue Inventory, which is the cutoff for moderate fatigue, will be eligible for the study. During the study period we will randomize and follow 171 survivors (we anticipate a ~13 % dropout with the goal of 150 completers). We hypothesize that persistently fatigued ovarian cancer survivors will experience improvements in fatigue, sleep, quality of life, and symptoms commonly associated with persistent fatigue from utilizing relaxing as compared to sham acupressure or no treatment.

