### Statistics Section.

The primary aim of this study is to investigate the differential effects of different modes of acupressure (relaxing vs. sham vs. no treatment) on fatigue as measured by the BFI in ovarian cancer survivors at week 6. The BFI, which measures the average degree of fatigue, gives a score that ranges between 0 and 10, with higher numbers indicating more fatigue. To investigate the difference in BFI between the three study arms, we shall use linear mixed-effects regression analysis with BFI as outcome, *week* as the within-subjects factor with four levels (0, 6, 12, 24) and *group* (relaxing acupressure, sham acupressure, no treatment) as the primary between-subjects factor. Of interest is the group-by-week interaction (to be included in the model), significance of which will indicate differences in extent of decrease between the arms. The covariate cancer stage at diagnosis and the interaction term group-by-stage will be added to models. Post-hoc sliced main effect of weeks within each study arm will be estimated. A *subject* random-effect will be used to account for the clustering effect within the four measurements on the same subject. Model diagnostics will be carried out to confirm the distributional assumptions and appropriate corrective actions (e.g. transformation) will be performed as needed. Models with more flexible covariance pattern (e.g. unstructured covariance, heterogeneity across groups) will be explored. An additional analysis with a spline version of weeks will be carried out which uses *week* as a continuous variable allowing one to estimate the rate of change in BFI.

A secondary analysis with BFI will also be carried out which investigates the difference in proportion of fatigued subjects ( $BFI \geq 4$ ) across the three study arms. The analytical framework will be that of a mixed-effects logistic regression model with presence of fatigue ( $BFI \geq 4$  yes/no) being the dichotomous outcome. Apart from group, week, and group-by-week interaction as primary covariates, the model will also be adjusted for baseline status of severity. Remaining covariates in the model are identical to those in the continuous BFI model. The clustering effect due to subject will be accounted for using a generalized estimating equations approach under a generalized linear mixed models framework.

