## 9.0 STATISTICAL METHODS

**Power Analysis.** Our power analysis is based on our primary aim to, “Examine the effect of 6 weeks of daily self-administered relaxing acupressure compared to self-administered sham acupressure or no treatment on persistent fatigue as measured with The Brief Fatigue Inventory.” Although we will run a larger model for the analysis, in the power calculation we focus on the specific components of the model in which we are interested. Towards that end, we compute the power via simulation using a mixed effects model with a between-subject factor group (3 levels), a within-subject factor week (0, 6, 12, and 24), group-by-time interaction and a random subject effect. The mean BFI at baseline is assumed to be 5.5, whereas values at end of treatment were assumed to be 4.5, 3.5, and 2, respectively for no treatment, sham acupressure and relaxing acupressure arms. The between-subject variance is assumed to be 4 at all time-points whereas the variance of the random subject component is taken to be 4 also (yielding an intra-class correlation of 0.5). These assumed values are estimates based on our pilot data. For this configuration, the power for detecting a significant week-by-group interaction is greater than 95% with a sample size of 50 evaluable participants per treatment arm (we anticipate a ~13 % drop out with the goal of 150 completers for a total sample size of 171) and a 5% level of significance. Such a model is able to detect a post-hoc difference between the relaxing acupressure and each of the other two arms with more than 90% power at a reduced 0.01 level of significance in order to protect against Type I error probability inflation. In the second phase after the treatment period, it is anticipated that both the no-treatment and the sham acupressure arms will experience a bounce

back close to the baseline level, while the relaxing acupressure arm will maintain its end-of-treatment average. Thus, the differences will be more pronounced than those in the active treatment phase, and we will be well

powered to detect the effect size.

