We also want to power the study to allow us to observe differences in sleep parameters. The extent of overlap between fatigue and sleep disturbances in ovarian cancer survivors is currently unknown. Research indicates that anywhere from 55 to 67% of ovarian cancer survivors experience sleep disruptions. While fatigued women are most likely enriched with individuals experiencing sleep disturbances we will conservatively assume that roughly 50% of women will have some significant sleep disturbances per treatment arm. As such, with 50 women per treatment group we will be overpowered for detecting a difference in fatigue and sufficiently powered to detect changes in sleep measures. For example, using the PSQI as a basis for powering differences in sleep quality from previous studies the mean PSQI in female cancer survivors ranges from  $6.84 \pm 0.376$  to  $7.16 \pm 0.325$ . A 1-point decrease in the PSQI from ~7 to ~6 is considered a clinically significant difference. The mean PSQI values at baseline is assumed to be 7 in all arms whereas the means are taken to be 7, 6, and 5 at 6 weeks in the no treatment, sham and relaxing acupressure arms, respectively. Assuming an intra-subject correlation of 0.5, we have powers above 95% to detect differences between any pair of arms at 1% level of significance.

All power calculations are carried out on the basis of 100 simulations in the software PASS 2008 (NCSS, Kaysville, Utah 84037, USA).

**9.1 Definition of an Evaluable Participant.** Evaluable participants must complete both the baseline and week 6 BFI.

**9.2. Post-hoc Power Analysis.** Average changes in BFI between baseline and 6 weeks for both true and sham acupressure were statistically significant at 5% level, so power was not an issue in detecting these effect sizes. It is evident from Table 4 that although it did not reach statistical significance, the difference between true and sham acupressure was trending towards that ( $p = 0.08$ ). It turns out that with the mean of the changes estimated to be that obtained in the data (Table 3), in order to detect a difference between the two Acupressure arms with 80% power, we would have needed 94 subjects per arm. The calculation is based on a two-sample t-test with a pooled standard deviation estimate of 1.7.

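### The weights for the conditional dropout sensitivity analysis are inverted: observed participants need 1/P(remaining observed), not 1/P(dropout)

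*Combined protocol and SAP*

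**What the plan says.** Under Handling Missing Data in the Statistics Section, the main answer to missing outcomes is the linear mixed model fitted to all available data. A second analysis is added under a condition, worded "If the proportion of dropouts is substantial (20% or more) in either arm". When that condition is met, the plan's instruction on weighting is this: "we shall also perform a weighted analysis with weights equal to the inverse of the probability of dropout".

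No other section redefines the weights, mentions the probability of staying in the study, or names a dropout model and its covariates. The two references in that paragraph belong to the multiple imputation text, so they do not settle what the weights mean. The paragraph also does not say whether weights are applied per visit or per participant.

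The primary test that this analysis would support is the group-by-week interaction for the Brief Fatigue Inventory (BFI), "significance of which will indicate differences in extent of decrease between the arms".

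**The concern.** Weighting for dropout works by letting the participants who stayed represent similar participants who left. Someone with a high risk of leaving who nevertheless stayed has to stand in for several others and needs a large weight. The stated rule does the reverse: the largest weights go to those with the smallest dropout risk, who have the fewest missing counterparts.

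This is a rule that is wrong as stated, not a missing detail. An analyst who follows it could obtain a weighted result that disagrees with a mixed model that is right, and conclude that the primary finding is sensitive to dropout. A sensitivity analysis is consulted when loss is heavy or unequal, which is when a false alarm or false reassurance does most harm.

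**Working it through.** The documents give no figure that depends on these weights, so there is nothing of the plan's own to reproduce. The check is algebra, then an illustration.

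**Algebra.** Let p be the dropout probability given covariates, and R = 1 if the outcome Y is observed, so P(R = 1) = 1 - p.

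- Weight 1/(1 - p): the expected weighted outcome is E[(1 - p) × Y/(1 - p)] = E[Y], the full-cohort mean.
- Weight 1/p: the net weight is (1 - p)/p, and the weighted mean is E[Y(1 - p)/p] / E[(1 - p)/p]. This generally differs from E[Y] when p varies with the outcome.
- No weighting: the net weight is 1 - p. Going from this to (1 - p)/p multiplies by 1/p, which falls as p rises. If p moves steadily with the outcome, the stated weights push the mean further in the direction in which completers are already biased.

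**Two-group example (assumed inputs).** Half the arm has mean BFI 2 and 10% dropout, half has mean 5 and 30% dropout. The true mean is 3.50.

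- Completers: (0.9 × 2 + 0.7 × 5)/(0.9 + 0.7) = 5.3/1.6 = 3.31
- 1/(1 - p): (2 + 5)/2 = 3.50
- 1/p: net weights 0.9/0.1 = 9 and 0.7/0.3 = 2.33, so (9 × 2 + 2.33 × 5)/11.33 = 2.62

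**Illustration on the plan's scale.** Inputs from the documents:

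- Baseline mean 5.5 and variances 4 and 4 (Section 9.0, "The between-subject variance is assumed to be 4 at all time-points", with 4 also for the random subject component). The total is 8, and the slope of week 6 on baseline is 4/8 = 0.5.
- Baseline limited to 4-10, from the entry rule ("have ≥4 on the Brief Fatigue Inventory, which is the cutoff for moderate fatigue") and the scale ("gives a score that ranges between 0 and 10, with higher numbers indicating more fatigue"). The truncated baseline has mean 6.52 and SD 1.57.
- Dropout of 20%, the plan's trigger.

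Assumed: logit(p) = a + b × (baseline - 5.5), with b = 0.1 to 0.3 and a set to give the overall rate. At 20% overall, p runs from 16% at BFI 4 to 26% at BFI 10 for b = 0.1, and from 10% to 40% for b = 0.3.

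Under the stated rule the net weight is (1 - p)/p = exp(-a - b × (baseline - 5.5)). The constant a cancels, so the bias with visit-level weights does not depend on the overall dropout rate. Bias in the week-6 arm mean, by numerical integration:

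| | b = 0.1 | b = 0.2 | b = 0.3 |
|---|---|---|---|
| As written, 1/p | -0.120 | -0.231 | -0.332 |
| Completers, 20% dropout | -0.025 | -0.050 | -0.074 |
| Completers, 28% dropout | -0.035 | -0.069 | -0.103 |
| Corrected, 1/(1 - p) | 0.000 | 0.000 | 0.000 |
| As written, variances 2 and 2 | -0.093 | -0.180 | -0.259 |

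The 28% row takes 1 - 41/57, the Table 3 count for true acupressure against the planned arm size; the number actually randomized is not given. The last row is included because variances 2 and 2 imply a change SD of 1.87, near the 1.5 to 2.0 in Table 3 ("Mean and standard deviation of changes between baseline and 6 weeks by study arm").

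**Change from baseline.** This is the quantity behind the interaction, and its bias changes sign with how the weights are applied.

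- Week 6 weighted, baseline unweighted: -0.12 to -0.33, as in the table.
- One weight per participant in a random-intercept model (simulation, 3.9 million participants, 20% dropout, b = 0.1 and 0.3): baseline shifts by -0.19 and -0.55, week 6 by -0.10 and -0.27, and change by +0.10 and +0.27. At 28% dropout the change bias is +0.09 and +0.25.

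The unweighted mixed model gives 0.00 throughout.

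**Sensitivity of the visit-level bias (b = 0.1 and 0.3).** With week-6 BFI also held to 0-10 around a mean parameter of 2: -0.10 and -0.28. With the entry rule applied at screening only and week 0 free over 0-10: -0.19 and -0.58.

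**The case against.** **The wording may be shorthand.** Nearby text is also loose, and many analysts would code standard weights without noticing. That is plausible, but nothing in the documents says so, and a plan is judged by what it tells the analyst to do.

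**The figures are for single arms, while the trial compares arms.** This stands. With visit-level weights and the same dropout slope, baseline distribution and baseline-to-week-6 regression in every arm, the bias is identical in all arms and cancels from the contrast, even if overall dropout differs. At b = 0.2 it is -0.231 at 10%, 20% and 28% dropout. A biased contrast needs a dropout mechanism, or a treatment effect by dropout risk, that differs between arms. The documents supply neither.

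**Size and sign rest on assumptions.** This also stands. The slopes are assumed and the sign for change depends on an unstated choice. Without the 4-10 limits on baseline, b = 0.2 takes a true week-6 mean of 3.50 to 2.70, a bias of -0.80 rather than -0.23. The algebra needs none of these inputs.

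**The reach is narrow.** Agreed: the analysis is additional and conditional. If dropout risk is constant within an arm, both weights give the same arm mean. The condition is not remote, though. If 57 were randomized to each arm as planned, the Table 3 counts of 41, 45 and 51 would leave 28%, 21% and 11% without a week-6 change score.

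**Conclusion.** The concern holds. The stated weights are the inverse of the wrong probability, and nothing elsewhere corrects them. If dropout risk moves steadily with the outcome, following the text moves weighted arm means further from the full-cohort value than not weighting completers at all. Under the assumed dropout slopes of 0.1 to 0.3, with baseline held to 4-10, the week-6 arm-mean error is -0.12 to -0.33 BFI points, about 4.5 to 5 times the completer error at 20% dropout (0.120/0.025 = 4.8; 0.332/0.074 = 4.5). Correct weights remove it.

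Severity is minor. The primary mixed model does not use these weights, the effect on between-arm differences is not quantified, and the documents do not show that the trigger was met or the analysis run. Confidence is high on the formula; the sizes are illustrative only.

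**What to change.** Redefine the weight so that each observed outcome counts as one over the estimated probability that the participant is still under observation at that visit (one minus the dropout probability), with that probability modelled from arm, baseline values and earlier observed outcomes. State that the weights are visit-specific. Because the trial has three arms, have the trigger refer to any of the three.

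Section 9.2 already reports week-6 results ("Average changes in BFI between baseline and 6 weeks for both true and sham acupressure were statistically significant at 5% level"), so the change should be labelled as a correction made after results were known. The sponsor should state whether the weighted analysis was run and with which weights. The cost is a few words, plus a re-run of this one sensitivity analysis if the stated weights were used.
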